(1) Futility: hydrocortisone may not prove effective for extubation or reduction of BPD. When approximately 50% and 75% of patients have been evaluated for the survival without BPD efficacy outcome at 36 weeks postmenstrual age, RTI will provide the DSMC with the information required to evaluate whether to stop the trial for futility. The analyses will include formal computation of conditional power for the primary outcome based on the observed data and the effect size and nuisance parameters used for the original study design and for key secondary parameters (including successful extubation during study drug administration, respiratory status at 40 weeks EGA, days on mechanical ventilation, days on positive pressure, days on oxygen, days exposed to open-label dexamethasone or other steroids (including inhaled steroids), length of stay, medications at discharge, growth parameters at 36 weeks EGA, nosocomial sepsis after study entry, necrotizing enterocolitis after study entry and retinopathy of prematurity) based on observed effect sizes and nuisance parameters. Should these analyses show a conditional power for the primary outcome of 0.1 or less and provide the DSMC with little evidence of a benefit for any of the secondary parameters, the DSMC will consider stopping enrollment in the trial for futility. Details for these futility analyses will be included in the DSMC monitoring plan. Patients who have been enrolled in the study will be followed through the 22 - 26month evaluation.

(2) Slow patient enrollment: A timeline for enrollment is proposed, above, based on eligible patients anticipated at the NRN centers. This will be monitored, and if patient enrollment does not meet expected, the reasons for the problem will be analyzed and the potential for study completion assessed. Study forms will be constructed to include reasons for lack of enrollment, to assist in this process.

BUDGET (not including RTI costs) based on 800 patients

Pharmacy cost (avg): \$2000/center set-up fee + \$500/year x 3 years =	\$ 56,000
Per patient (28 doses x \$20/dose) =	\$448,000*
Coordinator time: 10 hours/patient @ \$35/hr (\$350/pt)	\$280,000
Follow up (est. deaths 15%, follow up rate 90% = 612):	
\$400 GDB babies, \$700/pt otherwise (est.2/3)	\$367,200
Estimated total:	\$1,151,200

(*This may be lower, since all doses for each day can be prepared and dispensed at one time)

REFERENCES

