Bronchopulmonary dysplasia remains a leading morbidity of the extremely preterm infant, resistant to therapeutic interventions and associated with adverse neurodevelopmental outcomes (1-3). Most studies indicate that its rate of occurrence has not decreased in recent years (4), and several reports suggest that the incidence and/or severity of the disease may be increasing as postnatal glucocorticoid use has decreased (5-7). Although dexamethasone can facilitate extubation and decrease the incidence of BPD (8, 9), such treatment can be associated with increased risk of short- and long-term complications including impaired growth and neurodevelopmental delay (10 – 12). However, because BPD also is associated with increased risk for death and adverse neurodevelopmental outcomes, meta-analyses have suggested that in populations at high risk for death or BPD even dexamethasone therapy may be associated with net benefit (9, 13). Lower doses of dexamethasone may have equal pulmonary benefit with less toxicity (14 – 17); however, because it has a very long biologic half-life, suppresses endogenous cortisol production and disrupts the balance between mineralocorticoid and glucocorticoid in the brain (see below), dexamethasone may still be an inferior glucocorticoid choice for premature infants. Establishment of an alternative therapeutic agent to facilitate extubation may improve respiratory outcomes for these extremely preterm infants at very high risk for BPD, without the adverse effects previously seen with dexamethasone therapy.

HYPOTHESIS

Compared to placebo, hydrocortisone treatment of infants <30 weeks estimated gestational age at birth who remain on mechanical ventilation at 14 – 28 days postnatal age will significantly improve their rate of survival without moderate or severe BPD and will be associated with improvement in survival without moderate or severe neurodevelopmental impairment at 22 - 26months corrected age.

SPECIFIC AIMS

- To determine whether a 10 day course of hydrocortisone results in a significant increase in survival without moderate or severe BPD;
- To determine whether a 10 day course of hydrocortisone results in a significant increase in the number of infants successfully extubated during treatment;
- To determine whether this treatment affects other short-term outcomes including respiratory morbidities, growth and length of stay;

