(e) Concurrent therapy with indomethacin/ibuprofen: As stated above, infants who have received indomethacin or ibuprofen within 48 hours are not eligible for the study at that time. Spontaneous gastrointestinal perforation primarily occurs during the first 14 days of postnatal life; therefore, these infants should be at low risk for this event (34). However, to minimize any remaining risk, if a patient in this study is determined by the clinical care team to have developed a PDA during the intervention period which must be treated before study drug is completed, the attending physician may choose to stop the study drug prior to treatment with indomethacin or ibuprofen. If upon discontinuing study drug the patient becomes hypotensive and oliguric with an electrolyte profile consistent with adrenal insufficiency, the attending physician may choose to institute open-label hydrocortisone treatment or other clinically-indicated therapy for the hypotension.

(f) Clinical deterioration during study drug weaning: In this high-risk population, it is anticipated that some infants will experience clinical deterioration during or immediately following study drug therapy for unrelated causes, such as nosocomial sepsis, NEC or pneumonia. Although we do not anticipate that infants will experience clinical deterioration due to adrenal suppression during this short course of hydrocortisone, we will monitor for development of clinical signs of adrenal insufficiency during and immediately after treatment with study drug (see adverse event monitoring below). If an attending physician believes that the infant is experiencing hypotension with inadequate perfusion and oliguria (i.e., shock) due to adrenal insufficiency, a clinically-indicated blood specimen may be drawn for cortisol and the attending physician may institute therapies that he/she feels are clinically necessary for the care of the infant. Study drug should not be stopped for this occurrence. These events will be recorded on a study form created specifically for this study (to include above factors and attending physician judgment regarding the etiology of the event), and the event rate for such clinical deterioration in each group will be monitored by RTI and forwarded to the DSMC with other regularly transmitted study data.

(5) Post-extubation respiratory care

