(a) Respiratory support: Each center currently cares for these infants with techniques they feel appropriate, whether CPAP, CPAP with IMV, high-flow nasal cannula or other. This study will not prescribe the technique to be used. Because this is an RCT and because enrollment will be stratified by center and study treatment will be masked, the center-specific and attending-specific techniques should be balanced in both treatment groups equally over the course of the trial and therefore not introduce bias.

(b) Open-label glucocorticoid therapy

(i) Infants who remain successfully extubated are not to be treated with open-label glucocorticoids as therapy for BPD. This will be a protocol violation.

(ii) Infants who are not extubated during the study treatment period or who are subsequently re-intubated may be treated with open-label dexamethasone after ≥ 4 days following the last dose of study drug. Open-label dexamethasone will be encouraged to be prescribed as described by Doyle (15). Further treatment with HC for prevention/treatment of BPD will be considered a protocol violation. The rationale for this plan is as follows: (1) HC has not been demonstrated in an RCT to be efficacious for extubation, whereas dexamethasone has (8, 9, 15); (2) this design will permit a true RCT of HC without open-label contamination of the placebo group. At the same time, we will not be denying treatment to the group of infants that meta-analysis suggests derive net benefit from treatment with dexamethasone (13)

(6) Definition of successful extubation: An infant who remains extubated for at least one week, including at least 3 days (72 hours) after the last dose of study medication, will be considered to be successfully extubated in response to this treatment.

(7) Laboratory specimens: none

(8) Analysis of study outcomes

(a) Study specifications and definitions

(i). Analysis will be by intention to treat.

(ii) Moderate or severe BPD is defined as the need for supplemental oxygen by NRN physiologic definition at 36 weeks estimated gestational age. This includes an oxygen withdrawal test for infants receiving $<0.30\text{FiO}_2$, as described in the study manual of procedures. For this study, this determination will be made between 36⁰ to 36⁶ weeks.

(iii) Infants discharged on oxygen prior to 36 weeks gestation will be evaluated at 36 weeks gestational age at a follow-up clinic visit, a home visit or by telephone if necessary.

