The results indicate that if the improvement in the death or NDI outcome is only 1% on the hydrocortisone arm, then the probability of achieving a “success” on the safety outcome is 0.68 to 0.71 if success requires the lower limit of a 95% confidence interval on the risk benefit ratio to exceed 4, but 0.80 to 0.81 if we only require that the point estimate achieve 4. However, if the true benefit of the hydrocortisone treatment on death or NDI is at least 3% then the probability of achieving a “success” on the safety outcome is 0.83 to 0.86 if success requires the lower limit of a 95% confidence interval on the risk benefit ratio to exceed 4, and 0.90 to 0.93 if we only require that the point estimate achieve 4.

(d) Secondary outcomes and analysis: After analysis of unadjusted risk differences, other factors known to affect neurodevelopmental outcomes (such as gender, maternal education and dexamethasone exposure) will be entered into a multivariable analysis of outcome using the robust Poisson regression models described for the primary efficacy outcome for each of the binary secondary outcomes defined below. Secondary outcomes will include:

(i) Standard NRN measures of morbidity and growth as collected for the GDB at 36 weeks postmenstrual age and at 22 - 26 months corrected age. We will include ROP incidence and severity as a secondary outcome of specific interest, as there has been conflicting information regarding the relationship of dexamethasone to

ROP. We will also include a questionnaire to assess breathing outcomes at 22 - 26 months of age using forms developed for the SUPPORT study.

(ii) Successful extubation during the intervention period.

(iii) Use of open-label dexamethasone

(iii) Respiratory status at 40 weeks estimated gestational age. Assessment of respiratory outcomes at this age has been reported to more accurately predict long term respiratory outcomes (personal communication [name]). This assessment will not include a room air challenge, as repeating the physiologic testing would be burdensome and the 40 week status is not the primary study outcome.

(e) Concomitant medications will be recorded, in particular diuretics, bronchodilators, antibiotics, iNO, caffeine and Vitamin A.

(f) Safety monitoring:

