(i) Adverse events to be monitored include those previously associated with glucocorticoid therapy, such as hyperglycemia, hypertension and gastrointestinal perforation (8, 9, 34). Any infant who develops new, sustained hyperglycemia (>180mg/dl on at least two determinations at least 6 hours apart) or new, sustained hypertension (mean arterial pressure >95th percentile for age on four serial determinations over at least 12 hours (37)) may have study drug held or discontinued if, in the opinion of the attending neonatologist, there is no plausible alternative explanation for these findings (such as new thrombus). Delaying the study window to 14 days and excluding infants receiving indomethacin/ibuprofen in the preceding 48 hours should minimize the possibility for spontaneous GI perforation (34).

We will also specifically monitor for signs of adrenal insufficiency after study drug is discontinued, including hypotension and oliguria, as well as hyponatremia and hyperkalemia on clinically obtained electrolyte specimens. Previous studies of hydrocortisone at various doses have not reported these signs after discontinuation of a tapering course of the drug (18, 38-40 and personal communication [name] (22)). Patients who develop hypotension and oliguria (shock) significant enough in the judgment of the attending neonatologist to require support with volume and/or vasopressors may have a clinically indicated blood sample drawn for cortisol and may be restarted on hydrocortisone or other therapy for shock at the discretion of the clinical attending. Open-label hydrocortisone should be given at a test dose of 1mg/kg, with continuation of the therapy based on clinical response to the first dose.

(ii) Reporting of adverse events: In this high risk population, serious adverse events, such as nosocomial sepsis, respiratory deterioration or pneumonia, and death, occur with high frequency. Previously documented incidence and center variations in incidence of these serious adverse events in a similar population

(infants receiving mechanical ventilation at 14 days in the NRN benchmarking study) will be prepared and forwarded to the DSMC before patient enrollment begins.

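### Successful extubation is timed from the last dose of study drug, so for infants extubated early the success criterion depends on how much drug they received

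*Combined protocol and SAP*

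**What the plan says.** Section (6) defines success as applying to "An infant who remains extubated for at least one week, including at least 3 days (72 hours) after the last dose of study medication", and treats it as a response to the study treatment. It does not say whether the last dose is the actual or the scheduled one, has no clause for infants stopped early, and does not mention open-label steroid.

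Study drug can end early in either arm. Under section (8)(f)(i), infants with new sustained hyperglycemia or hypertension "may have study drug held or discontinued if, in the opinion of the attending neonatologist", no other explanation is plausible. Under section (4)(e), if a PDA must be treated, "the attending physician may choose to stop the study drug prior to treatment with indomethacin or ibuprofen".

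The window for the outcome is worded in three ways:
- Specific Aims: a "significant increase in the number of infants successfully extubated during treatment";
- section (8)(d)(ii): "Successful extubation during the intervention period";
- Possible problems (1), Futility: "including successful extubation during study drug administration".

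None says whether the window of an infant stopped early closes at the stop or at day 10.

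Section (5)(b)(ii) also runs from the last dose. Infants not extubated in the study treatment period, or later re-intubated, "may be treated with open-label dexamethasone after ≥ 4 days following the last dose of study drug".

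**The concern.** The length of the success requirement is set by an event after randomisation, namely when dosing ended. Take two infants extubated 2 days after the first dose and re-intubated at day 10. The one who completed the course is a failure, because 72 hours have not passed since the last dose. The one whose drug stopped at day 4 is a success. This sits badly with the intention-to-treat principle in section (8)(a)(i).

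If early stopping is commoner in one arm, the comparison is distorted. Section (8)(f)(i) names hyperglycemia and hypertension as previously associated with glucocorticoids, so a difference is conceivable.

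Early stopping can also undo the separation from dexamethasone that the design gives infants who complete the course. At stake are the second specific aim, a listed secondary outcome and one of the parameters shown to the DSMC for futility.

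**Working it through.** **Inputs.** The taper is in section (4)(c); the one-week and 72-hour requirements in section (6); the 4-day dexamethasone interval in section (5)(b)(ii). The plan gives no figure for extubation success and no early-stop rates.

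**Dose count.** 4 × 2 + 4 × 3 + 2 × 3 + 1 × 2 = 8 + 12 + 6 + 2 = 28 doses over 10 days, matching the 28 in the Budget. Counting t in days from the first dose, with each dose at the start of its interval, dose 28 falls at t = 9. For a completer the 72 hours end at t = 12.

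**Extubated time required** = max(7, t_last + 3 − t_extubation) days.

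| Extubated at t | Completer (t_last = 9) | Stopped at t = 4 | Difference |
|---|---|---|---|
| 1 | 11 | 7 | 4 |
| 2 | 10 | 7 | 3 |
| 3 | 9 | 7 | 2 |
| 4 | 8 | 7 | 1 |
| 5 or later | 7 | 7 | 0 |

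Early extubation matters here because section (4)(d) calls for an attempt within 72 hours of starting drug.

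**Dexamethasone.** For a completer it opens at t = 9 + 4 = 13, after the 72 hours end at t = 12, so it cannot assist an extubation made during the course. After a stop at t = 2, 3, 4 or 5 it opens at t = 6, 7, 8 or 9, inside a nominal 10-day window. After a stop at t = 6 it opens at t = 10 and the route closes. For example, an infant is extubated at t = 2, stopped at t = 3, re-intubated at t = 4, given dexamethasone from t = 7, extubated at t = 9 and stays extubated a week. Under a nominal window this infant meets section (6). If the window is actual dosing, it closed at t = 3 and the route contributes nothing.

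**Size, on assumed rates only.**
- Overall: bias = (stop rate on hydrocortisone − stop rate on placebo) × fraction of early stoppers reclassified. With 5–15% against 2–5% and 10–30% reclassified, the minimum is (0.05 − 0.05) × 0.10 = 0 and the maximum (0.15 − 0.02) × 0.30 = 3.9 points.
- Timing alone: with a daily re-intubation risk h of 2–8% and extubation at t = 1–3, the gain from a stop at t = 4 is (1 − h)^7 − (1 − h)^(required days for a completer). This runs from 0.868 − 0.834 = 0.034 (h = 2%, t = 3) to 0.558 − 0.400 = 0.158 (h = 8%, t = 1). If 2–10 points more infants stop early on hydrocortisone, all extubated by t = 3, the spurious difference is 0.02 × 0.034 = 0.07 to 0.10 × 0.158 = 1.6 points.
- Dexamethasone alone, nominal window: the same excess, with 50–80% of those infants intubated at the stop and 10–50% of these extubated on dexamethasone before day 10, gives 0.02 × 0.5 × 0.1 = 0.1 to 0.10 × 0.8 × 0.5 = 4 points. This counts every intubated infant; counting only the re-intubated would give less. Under an actual-dosing window it is 0.

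**The case against.** The best reply is that no bias towards hydrocortisone has been shown, and much of it stands.

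- **Side effects by arm.** Risks (2) says these effects were not seen in earlier hydrocortisone trials against placebo. The Rationale describes early trials at 1–2 mg/kg/day, while section (4)(c) starts at 4 mg/kg/day, so a difference is not ruled out, but it is not evidenced either. Stops for PDA treatment have no stated link to arm.
- **The window can reverse the effect.** If it closes with actual dosing, an infant stopped at t = 4 has only 4 days in which to be extubated, which works against the arm with more stops.
- **Held doses.** Section (8)(f)(i) allows drug to be held as well as discontinued. If held doses are made up and the last dose moves to t = 10, an infant extubated at t = 2 needs 10 + 3 − 2 = 11 days, a harder test. The protocol does not say whether they are made up.
- **Limited reach.** The one-week minimum always applies and nothing changes for extubations from about day 5.
- **Dexamethasone is partly handled.** Its use is a secondary outcome and exposure to it enters the multivariable models in section (8)(d). That does not change how an infant is scored.

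A reader might also infer that an infant never extubated before an early stop could readily gain the dexamethasone credit. That needs the study treatment period to end at the stop for eligibility while the outcome window runs to day 10. On either consistent reading it fails. The route is consistent only for re-intubated infants.

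What the reply does not remove is that the rule scores the same respiratory course differently according to drug received, even with equal stop rates.

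**Conclusion.** The defect is real and limited. With the last dose read as the actual one, an early stop cuts the required extubated time by up to 4 days for infants extubated from t = 1 to t = 4, and by nothing from about day 5. With a nominal 10-day window and a stop by about day 5, a dexamethasone-assisted extubation in a re-intubated infant can be credited to study drug.

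A reader might infer that the rule inflates success on hydrocortisone. The documents do not support that: they give no stop rates, point both ways on side effects, and leave open the window that fixes the direction. The range of 0 to about 4 percentage points rests wholly on assumed rates and includes no bias.

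The primary outcome and its sample size are unaffected. In the futility review, extubation is one of many secondary parameters considered alongside conditional power for the primary outcome. The definition should still be corrected before analysis, since the present one does not treat all randomised infants alike.

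**What to change.** Change the outcome definition only, with one clock from the first dose for every infant, whatever drug was received. Success would mean:
- extubated within the scheduled 10-day period;
- alive and extubated for at least 7 consecutive days; and
- still extubated 72 hours after the scheduled time of the final dose, about 12 days after the first dose.

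The timing rule is then unchanged for infants who complete on schedule. The end point should be written as 72 hours after the scheduled final dose: running it to the end of day 13 would add about a day for completers.

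Score open-label systemic glucocorticoid for BPD before that point as non-success, with a sensitivity analysis that ignores it. Use the same window in the Specific Aims, section (6), section (8)(d)(ii) and the futility paragraph.

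The cost is one reworded definition and three matching edits. Extubation, re-intubation and steroid dates are already needed for the listed outcomes, so there are no new data, and care does not change.
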